**Table 8.c Dose Modification Recommendations for Modakafusp Alfa Hematological Toxicities**

*This table does not include guidance for management of bleeding TEAEs and IRRs. Refer to Table 8.d for the management of bleeding TEAEs and Table 8.g and Table 8.h for the management of IRRs.*

Criteria	Action
Grade 1 and 2 AEs	No dose reductions or interruptions.
Grade 3 and 4 AEs	
Hold modakafusp alfa next infusion until resolution to Grade <math>\leq 2</math> then resume treatment.
 
Consider growth factors and/or transfusion according to local practice when clinically indicated. Please refer to Section 8.6.1.2 for the criteria of starting a new cycle of treatment.
 
If the next cycle of modakafusp alfa is delayed for <math>>14</math> days, study treatment should be discontinued unless the investigator considers that the patient will receive benefit continuing in the study.

AE: adverse event; IRR: infusion-related reaction; TEAE: treatment-emergent adverse event.

This table does not include guidance for the management of bleeding TEAEs, which is found in Table 8.d or for the management of IRRs, which is found in Table 8.g, Table 8.h, and Section 8.10.1.1.

**Table 8.d Dose Modification Recommendations for Modakafusp Alfa Bleeding TEAEs**

*This table does not include guidance for management of IRRs. Refer to Table 8.g and Table 8.h for the management of IRRs.*

Criteria	Action
Grade 1 and 2	No dose reductions or interruptions. Treat according to local practice.
Grade 3 without associated Grade 4 thrombocytopenia	
Hold next infusion of modakafusp alfa until resolution to Grade <math>\leq 1</math> or baseline, and then resume treatment.
 
Subsequent occurrence: Discontinue modakafusp alfa.

Grade 3 with associated Grade 4 thrombocytopenia	Discontinue modakafusp alfa.
Grade 4	Discontinue modakafusp alfa.

IRR: infusion-related reaction; TEAE: treatment-emergent adverse event.

This table does not include guidance for the management of IRRs, which is found in Table 8.g, Table 8.h, and Section 8.10.1.1

**8.6.1.4 Criteria for Dose Reduction**

When a dose reduction occurs, the modakafusp alfa dose will be reduced to the next lower dose that has been established as a safe dose during dose escalation (Table 8.e). In general, after a dose is reduced, it should not be re-escalated even if there is minimal or no toxicity with the reduced dose. However, if further evaluation reveals that the AE that led to the dose reduction was not study drug related, the dose may be re-escalated to the original dose level.

**Table 8.e Dose Reduction Levels for Modakafusp Alfa**

Starting Dose	80 mg	120 mg	240 mg
First dose level reduction	60 mg	80 mg	120 mg
Second dose level reduction	Discontinue treatment	60 mg	80 mg
Third dose level reduction	NA	NA	60 mg

NA: not applicable.

#### **8.6.1.5 Criteria for Discontinuation**

In the dose escalation, modakafusp alfa should be discontinued in patients experiencing an AE in Cycle 1 meeting criteria for a DLT for which the investigator considers that retreatment of the patient could be dangerous.

If the next cycle of modakafusp alfa is delayed for >14 days because of modakafusp alfa-related toxicities, study treatment should be discontinued unless the investigator considers that the patient will receive benefit continuing in the study. If treatment discontinuation is determined, the EOT visit should be completed within 30 days (+10 days) after the last administration of modakafusp alfa.

Patients who discontinue modakafusp alfa because of TEAEs assessed by the investigator as related *only* to modakafusp alfa may continue daratumumab SC treatment at the discretion of the investigator and with agreement by the sponsor.

#### **8.6.2 Combination Drug**

Dose modification, if any (dose change, interruption, discontinuation, etc.) of the combination drug (daratumumab SC) should be done in accordance with the drug's local prescribing information. Alternative dose modifications may be recommended after discussion with the investigator and sponsor to maximize exposure of study treatment while protecting patient safety.

#### **8.7 Prohibited Concomitant Medications and Procedures**

The following medications and procedures are prohibited during the study:

- Radiation therapy for disease under study. Local radiotherapy for bone pain is permitted after agreement with the sponsor and once progressive disease is ruled out.
- Any investigational agent other than modakafusp alfa or the study combination agents, including agents that are commercially available for indications other than MM that are under investigation for the treatment of MM.
- Concomitant chronic corticosteroid administration of >10 mg of prednisone or equivalent unless given as treatment or prophylaxis for IRRs, as premedication for administration of certain blood products or for exacerbations of respiratory tract disorders, acute pain

management, suspected or confirmed immune-mediated thrombocytopenia, or if tumor flare is suspected.

- Live vaccines are not recommended.

## 8.8 Permitted Concomitant Medications and Procedures

All necessary supportive care consistent with optimal patient care will be available to patients as necessary. All blood products and concomitant medications will be recorded in the electronic case report forms (eCRFs) as specified in the SOEs ([Appendix A](#)).

The following medications and procedures are permitted while the patient is receiving the study drug:

- Myeloid growth factors (eg, granulocyte colony stimulating factor, granulocyte macrophage-colony stimulating factor) and erythropoietin are permitted. Their use should follow the product label, published guidelines, and institutional practice. Granulocyte colony stimulating factor is allowed to accelerate the recovery of neutropenia to enable the start of a new cycle ([Section 8.6.1.2](#)).
- Patients should be transfused with RBCs and platelets as clinically indicated. Transfusions must be recorded in the concomitant procedure pages of the eCRF. Platelet transfusion should not be applied only for the purpose of meeting the treatment criterion of platelet count to start a new cycle.
- Concomitant treatment with bisphosphonates or monoclonal antibodies like denosumab will be encouraged for all patients with evidence of lytic destruction of bone or with osteopenia, according to the American Society of Clinical Oncology Clinical Practice Guidelines or institutional practice in accordance with the product label, unless specifically contraindicated. If bisphosphonate therapy was not started before the study start, it should be initiated as soon as clinically indicated.
- Topical or inhaled steroids (eg, for the treatment of asthma) are permitted.
- Systemic steroids for acute management of pain, suspected or confirmed immune-mediated thrombocytopenia or other disease or treatment-related complications are permitted.
- Plasmapheresis.
- IV immunoglobulins usage is acceptable for prolonged Grade 4 transfusion-dependent thrombocytopenia, hypogammaglobulinemia, or other investigator criteria if it is considered that there is an underlying autoimmune mechanism.
- Thrombopoietin agonists are also allowed for thrombocytopenia management at the investigator's discretion.

## 8.9 Precautions and Restrictions

### 8.9.1 Contraception and Pregnancy Avoidance Procedures

It is not known what effects modakafusp alfa has on human pregnancy or development of the embryo or fetus; therefore, patients participating in this study should avoid becoming pregnant or avoid impregnating a partner and should not donate sperm or ova. Patients of reproductive potential should use effective methods of contraception through defined periods during and after study treatment as specified below.

Reproductively female patients must meet 1 of the following:

- Postmenopausal for at least 2 years before the screening visit, OR
- Surgically sterile, OR
- If they are of childbearing potential, agree to practice 1 highly effective method and 1 additional effective (barrier) method of contraception (see [Table 8.f](#)) at the same time, from the time of signing of the ICF through 3 months after the last dose of daratumumab SC, or 7 days after the last dose of modakafusp alfa, whichever is longer, OR
- Agree to practice true abstinence, when this is in line with the preferred and usual lifestyle of the patient during the entire study treatment period and through 3 months after the last dose of daratumumab SC, or 7 days after the last dose of modakafusp alfa, whichever is longer. (Periodic abstinence [eg, calendar, ovulation, symptothermal, postovulation methods], withdrawal, spermicides only, and lactational amenorrhea are not acceptable methods of contraception. Female and male condoms should not be used together.)
- Agree not to donate an egg or eggs (ova) or breastfeed a baby during the study through 3 months after the last dose of daratumumab SC or 7 days after the last dose of modakafusp alfa, whichever is longer.
- Must also adhere to any applicable local (country-specified) treatment-specific pregnancy prevention guidelines.

Reproductively male patients, unless surgically sterilized (ie, status postvasectomy), must agree to 1 of the following:

- Agree to practice effective barrier contraception (see [Table 8.f](#)) during the entire study treatment period and through 7 days after the last dose of modakafusp alfa, OR
- Agree to practice true abstinence, when this is in line with the preferred and usual lifestyle of the patient during the entire study treatment period and through 7 days after the last dose of modakafusp alfa. (Periodic abstinence [eg, calendar, ovulation, symptothermal, postovulation methods], withdrawal, spermicides only, and lactational amenorrhea are not acceptable methods of contraception. Female and male condoms should not be used together.)
- Agree not to donate sperm during the study and for 7 days after the last dose of modakafusp alfa

- Must also adhere to any applicable local (country-specified) treatment-specific pregnancy prevention guidelines.

**Table 8.f      Highly Effective Methods of Contraception**

Highly Effective Methods	Additional Effective (Barrier) Methods
Combined (estrogen and progestogen containing) hormonal contraception associated with inhibition of ovulation 

• Oral

• Intravaginal

• Transdermal

	Male or female condom with or without spermicide (female and male condoms should not be used together)
Progestogen-only hormonal contraception associated with inhibition of ovulation 

• Oral

• Injectable

• Implantable

	
Intrauterine device	
Intrauterine hormone-releasing system	
Bilateral tubal occlusion	Cap, diaphragm, or sponge with spermicide
Vasectomized partner	
Sexual abstinence	

### **8.9.2      Pregnancy**

Any participant who is found to be pregnant during the study should be withdrawn and modakafusp alfa should be immediately discontinued. In addition, any pregnancies in the partner of a study participant during the study should also be recorded, after authorization from the study participant's partner.

If a participant or a study participant's partner agrees to their primary care physician being informed, the investigator should notify the primary care physician that the participant was participating in a clinical study at the time of the pregnancy and provide details of the study drug the subject received.

All pregnancies, including those in partners of study participants, will be followed up to final outcome using the pregnancy form. The outcome, including any premature termination, must be reported to the sponsor. An evaluation after the birth of the child will also be conducted.

### **8.10      Management of Clinical Events**

If dose alterations are necessary as a result of the events detailed below, [REDACTED]

## 8.10.1 Modakafusp Alfa

### 8.10.1.1 IRRs

An IRR is a reaction that develops during or shortly after administration of a drug, and with modakafusp, an IRR can occur during any cycle. Signs and symptoms may include pruritus, urticaria, fever, rigors/chills, diaphoresis, bronchospasms, and cardiovascular collapse. In this study, IRRs are designated as AESIs.

It is mandatory that all patients receive premedication, including corticosteroids, before modakafusp alfa dosing (Section 8.1.1.3). Recommendations for premedications for the combination agent daratumumab SC are detailed in Section 8.1.2.3. On days on which the combination agent is administered on the same visit day as modakafusp alfa, administer the modakafusp alfa-specific premedication only.

If a patient presents with an IRR at any dose level, the duration of the infusion of modakafusp alfa may be extended per investigator's discretion. Total time from modakafusp alfa dosing solution preparation until end of infusion must not exceed 7 hours. Infusion and pharmacy staff are advised to be prepared accordingly for either a planned, extended infusion time or for potential infusion interruptions. See the IB and pharmacy manual for additional guidance.

Patients should be carefully observed during modakafusp alfa infusions. Trained study staff at the clinic should be prepared to intervene in case of any IRRs, and resources necessary for resuscitation (eg, agents such as epinephrine and aerosolized bronchodilators and medical equipment such as oxygen tanks, tracheostomy equipment, and a defibrillator) must be available at bedside.

In case of an IRR, a serum sample for circulating biomarkers, a blood sample for flow cytometry, a blood sample for RNA, and a serum sample for immunogenicity (ADA) should be collected, if clinical management of the patient allows (as detailed in the SOEs in [Appendix A](#)).

Patients will be advised to promptly report signs and symptoms that may indicate IRRs, including fever, chills, dizziness, nausea, vomiting, flushing, cough, headache, and rash during or soon after end of infusion.

If the patient continues on treatment, premedication and postinfusion medication should be considered for future modakafusp alfa administrations per Section 8.1.1.

All IRRs, including the signs and symptoms, will be reported in the eCRF per completion guidelines.

Serious AESIs will be reported to Takeda Global Pharmacovigilance in an expedited manner within 24 hours.

### **Grade 1 and 2 IRRs**

The recommendations for managing Grade 1 and Grade 2 IRRs are presented in [Table 8.g.](#)

**Table 8.g Recommendations for Managing Grade 1 and Grade 2 IRRs**

IRR	Action
Grade 1 or 2	The infusion should be paused. When the patient's condition is stable, infusion may be restarted at the investigator's discretion. On restart, the infusion rate should be half of that used before the interruption. Subsequently, the infusion rate may be increased at the investigator's discretion.
Grade 2 event of laryngeal edema, or Grade 2 event of bronchospasm that does not respond to systemic therapy.	Patient must be withdrawn from treatment if the event does not resolve within 6 hours from onset.

IRR: infusion-related reaction.

### **Grade 3 or Higher IRRs**

The recommendations for managing Grade  $\geq 3$  IRRs are presented in [Table 8.h](#).

**Table 8.h Recommendations for Managing Grade  $\geq 3$  IRRs**

IRR	Action
Any Grade 4 event:	Patient must be withdrawn from treatment.
Grade 3 bronchospasm or laryngeal edema:	Patient must be withdrawn from treatment.
Grade 3 event other than bronchospasm or laryngeal edema:	Infusion must be stopped, and the patient must be observed carefully until resolution of the IRR.
If the intensity of the IRR remains at Grade 3 after 2 hours:	Patient must be withdrawn from treatment.
If the intensity of the IRR decreases to Grades 1 or 2:	Infusion may be restarted at the investigator's discretion. Within 2 hours of restart, the infusion rate should be half of that employed before the interruption. Subsequently, the infusion rate may be increased at the investigator's discretion.
If the intensity of the IRR returns to Grade 3:	The procedure described above may be repeated after restart of the infusion at the investigator's discretion.
If the intensity of the IRR increases to Grade 3 for a third time:	Patient must be withdrawn from treatment.

IRR: infusion-related reaction.

#### **8.10.1.2 Low Platelet Count**

Treatment decisions will be based on patient platelet counts assessed before any transfusion. Low platelet counts (Grade 4) should cause scheduled infusions to be postponed or to be permanently discontinued. If at any time the platelet count is less than  $10 \times 10^9/L$  after initiation of modakafusp alfa treatment, the patient should be withdrawn from modakafusp alfa treatment unless clinical benefit is observed and the investigator considers that thrombocytopenia can be managed, including with dose modifications. Dose modification for bleeding TEAEs should follow the recommendations included in [Table 8.d](#). The investigator can consider the usage of

corticosteroids, IV immunoglobulins or thrombopoietin agonists in selected cases depending on severity, duration, transfusion requirements, and additional risk factors for bleeding and based on the suspected underlying mechanism. Platelet transfusion and daily monitoring of platelet counts are recommended.

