### **8.6.1.3 Criteria for Dose Interruption**

All toxicities that occur during the study will be actively managed following the standard of care unless otherwise specified in the protocol. Patients experiencing AEs attributed to modakafusp alfa may continue study treatment with the same dose, may have modakafusp alfa treatment held, may have their dose reduced, or may be permanently discontinued from the study. Patients who have study drug held because of treatment-related or possibly related AEs may resume study drug treatment after resolution of the AE at the same dose level or at a reduced dose, depending on the nature and severity of the AE and whether it is the first occurrence or is recurrent.

**Table 8.b** and **Table 8.c** provide general dose modification recommendations for nonhematologic and hematologic toxicities, respectively. **Table 8.d** provides dose modification recommendations for bleeding TEAEs to mitigate the risk of fatal hemorrhagic events. If the modakafusp alfa dose is withheld on the basis of these criteria, clinical and laboratory re-evaluation should be repeated at least weekly or more frequently, depending on the nature of the toxicity observed, until the toxicity resolves to Grade  $\leq 1$  or baseline. If there are transient laboratory abnormalities that, based on investigator assessment, are not clinically significant or drug related, continuation of therapy without dose modification is permissible on discussion with the sponsor.

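### Platelets below 10 × 10⁹/L that recover without a delay of more than 14 days: a patient who fails the Section 8.10.1.2 exception is withdrawn under that section but re-dosed under Table 8.c

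*Protocol*

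**What the plan says.** Protocol Section 8.10.1.2 (Low Platelet Count) has two layers. For Grade 4 counts in general: "Low platelet counts (Grade 4) should cause scheduled infusions to be postponed or to be permanently discontinued". For a lower threshold it adds a stricter rule. "If at any time the platelet count is less than" 10 × 10⁹/L once modakafusp alfa has been started, "the patient should be withdrawn from modakafusp alfa treatment unless clinical benefit is observed and the investigator considers that thrombocytopenia can be managed". The exception therefore has two conditions, both of which must hold. The section adds that dose modification may be part of managing the thrombocytopenia.

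Table 8.c (Section 8.6.1.3) covers hematologic toxicities. Its row for Grade 3 and 4 events reads "Hold modakafusp alfa next infusion until resolution to Grade" 2 or lower, after which treatment resumes. It has one limit on resuming. If the next cycle is delayed by more than 14 days, "study treatment should be discontinued unless the investigator considers that the patient will receive benefit continuing in the study". It also states what it leaves out: "This table does not include guidance for management of bleeding TEAEs and IRRs". It refers the reader to Tables 8.d, 8.g and 8.h and to Sections 8.6.1.2 and 8.10.1.1.

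Section 8.6.1.3 introduces Tables 8.b and 8.c as ones that "provide general dose modification recommendations for nonhematologic and hematologic toxicities, respectively". The sentence that opens Section 8.10 begins by addressing dose alterations for the events that follow. The rest of it is redacted.

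**The concern.** Two places in the protocol govern the same laboratory event, and for some patients their default actions are opposite. A site that starts from the dose-modification table has no visible route to the stricter platelet rule. The table cites Section 8.10.1.1 (infusion-related reactions) but not the next section, 8.10.1.2, which deals with low platelets.

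The first consequence is for patient safety. Section 4.5.2.1 names thrombocytopenia as an expected overlapping toxicity of the combination. Section 8.6.1.3 shows how seriously the protocol takes bleeding, since Table 8.d "provides dose modification recommendations for bleeding TEAEs to mitigate the risk of fatal hemorrhagic events". Table 8.d covers bleeding events themselves. The question here is the low count that it does not settle.

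The second consequence is for the data. If sites handle the same count differently, this affects the summaries of treatment discontinuation, dose modification and exposure (Protocol Section 13.1.8; SAP Sections 6.5 and 6.7.1). It also affects whether a re-dosed patient is recorded as a protocol deviation. Sample size and the precision of the response rate are not affected.

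**Working it through.** The plan gives no figure to reproduce. The check is a unit conversion followed by a comparison of the two rules.

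**Step 1: do both rules apply to the same patient?** Section 8.3.1 defines Grade 4 thrombocytopenia as platelets below 25,000/mm³. The Section 8.10.1.2 threshold converts as 10 × 10⁹/L = 10,000/mm³. Since 10,000 < 25,000, every count below 10 × 10⁹/L is Grade 4 and falls in the Grade 3 and 4 row of Table 8.c. The overlap is complete.

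**Step 2: does the table's reference to Section 8.6.1.2 resolve it?** Section 8.3.1 gives Grade 3 or worse as below 50,000/mm³, so recovery to Grade 2 or lower means at least 50,000/mm³. That is also the platelet criterion in Section 8.6.1.2 for starting a new cycle. A patient who has recovered that far passes it. Section 8.6.1.2 says nothing about an earlier count below 10 × 10⁹/L.

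**Step 3: set the rules side by side.**

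| After a count below 10 × 10⁹/L | Section 8.10.1.2 | Table 8.c | Result |
|---|---|---|---|
| Both exception conditions met; recovery to Grade ≤2, delay not over 14 days | May continue | Resume | Agree |
| Either condition unmet; same recovery | Withdraw from modakafusp alfa | Resume | Conflict |
| Next cycle delayed more than 14 days | Withdraw unless both conditions are met | Discontinue unless the investigator expects benefit | Same default |

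In the third row the exceptions are worded differently: Table 8.c does not require the thrombocytopenia to be judged manageable. The default is still the same.

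Grade 4 counts of 10 × 10⁹/L or more do not conflict. Section 8.10.1.2 allows postponement there, which is compatible with holding and resuming.

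**Step 4: can the conflicting row occur?** Section 4.5.1.2 reports that, with the single agent at 1.5 mg/kg Q4W, mean platelet counts were lowest at Day 8 or 15 of the first two cycles. In most cases they recovered in time for the next cycle. In the Schedules of Events (Appendix A, Tables 1 and 3) the first post-baseline investigator response assessment is at Cycle 2 Day 1. For a Cycle 1 nadir, the decision to re-dose can therefore fall due when benefit has hardly had a chance to be observed, so the first exception condition may well be unmet. These means describe timing only. They do not show how often a count falls below 10 × 10⁹/L.

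**The case against.** The strongest reply is that this is a general rule with a specific rule on top. Section 8.6.1.3 calls Table 8.c general, and the same section says that patients with attributed events may be held, reduced or permanently discontinued. Section 8.10.1.2 is a dedicated section with a narrower trigger that applies at any time. A site that reads both can follow both by applying the narrower one. This reading is plausible, but no visible text states it, and a reader who starts from Table 8.c is not sent to Section 8.10.1.2.

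The redactions limit what can be said. The lead-in to Section 8.10 is where a precedence rule could sit. Section 8.5 and the second change in the Amendment 2 summary are also blacked out. A reader might infer that the protocol leaves the two rules unranked. The documents do not support that, because redacted text is not missing text. What can be said is that Table 8.c, as visible, has no pointer.

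Three other inferences also go too far:

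- **Table 8.c resumes dosing without any limit.** It does not: it has the rule for delays over 14 days and the exclusions for bleeding events and infusion-related reactions. What it lacks is an exception for platelets below 10 × 10⁹/L.
- **Every patient below 10 × 10⁹/L is caught between the rules.** Only the second row of the comparison conflicts.
- **Section 8.6.1.5 is deficient because it omits the platelet criterion.** That section is not an exhaustive list. It also leaves out the discontinuation rules in Tables 8.b, 8.d, 8.g and 8.h.

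**Conclusion.** The inconsistency is real but narrow. It concerns a patient whose platelets fall below 10 × 10⁹/L, who does not meet both exception conditions, and whose count recovers to Grade 2 or lower without a delay of more than 14 days. For that patient the visible text of Section 8.10.1.2 and that of Table 8.c give opposite default actions. This rests on the visible text only and assumes nothing about the redacted sentences.

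The number of patients affected cannot be estimated. A reader might take the 16.7% rate of Grade 4 thrombocytopenia in Section 4.1.2.2 (N = 30) and compute 0.167 × 18 = 3.0 phase 1 patients. The documents do not support using that figure as the size of the affected group:

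- It is a single-agent rate at 1.5 mg/kg Q4W, which Section 4.1.2.2 equates to 120 mg. Phase 1 gives the combination, starts at 80 mg, and may use 60 to 240 mg.
- It counts all Grade 4 events. The share below 10 × 10⁹/L is not given and could be anything from none to all.
- It takes no account of whether the exception is met or how quickly counts recover.

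Appendix G also records the sponsor's 2023 decisions not to proceed to phase 2a and to discontinue development, so few patients may be affected. The point still merits correction, because it bears on patient safety and the remedy is small.

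**What to change.** The sponsor should reconcile Table 8.c with Section 8.10.1.2 so that one action applies to platelets below 10 × 10⁹/L, and should add a cross-reference to Section 8.10.1.2 in Table 8.c. If the redacted lead-in to Section 8.10 already says which rule governs, the cross-reference alone may be enough. Which action applies is for the sponsor to decide, and this review takes no view on it.

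The cost is protocol wording. Sample size, endpoints and planned analyses stay as they are.
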